## 6.2.2 Serious Adverse Events

An SAE must be recorded on the SAE Form. An SAE requires expeditious handling to comply with regulatory requirements. Any SAEs occurring from the signing of the ICF through 30 days after the last dose of study drug or the end of the study, whichever is longer, will be captured and must be reported within 24 hours after the investigator is made aware of the event.

### 6.2.2.1 Serious Adverse Event Definition

An SAE is defined as an AE that results in any of the following outcomes:

- Death
- Is life-threatening. A life-threatening AE is any AE that places the subject – in the investigator’s opinion – at immediate risk of death from the reaction as it occurred. It does not include a reaction that, had it occurred in a more serious form, might have caused death.
- Persistent or significant incapacity or substantial disruption of ability to conduct normal life functions
- Hospitalization or prolongation of existing hospitalization
- Congenital anomaly/birth defect

- Important medical events that may not result in death, be life-threatening, or require hospitalization may be considered an SAE when, based upon appropriate medical judgment, they may jeopardize the subject or may require medical or surgical intervention to prevent one of the other outcomes listed in this definition. Examples of such medical events include allergic bronchospasm requiring intensive treatment in an emergency room or at home, blood dyscrasias or convulsions that do not result in hospitalization, or the development of drug dependency or drug abuse.

Scheduled and/or elective hospitalizations occurring under the following circumstances will not be defined as SAEs for this clinical study:

- Planned before entry into the clinical study
- Elective treatment of a condition unrelated to the studied indication or its treatment
- Occur on an emergency, outpatient basis and do not result in admission (unless fulfilling the previous criteria)
- Part of the normal treatment or monitoring of the studied indication and not associated with any deterioration in condition

### 6.2.2.2 Procedures for Reporting Serious Adverse Events

All initial and follow-up SAE reports must be reported by the investigator to the sponsor's Global Drug Safety Department and the CRO/Shire Medical Monitor within 24 hours of the first awareness of the event. Note: The 24-hour reporting requirement for SAEs does not apply to reports of abuse, misuse, overdose, or medication errors (see Section 6.2.1.1) unless they result in an SAE.

The investigator must complete, sign, and date the sponsor's Clinical Study Serious Adverse Event and Non-serious AEs Required by the Protocol Form and verify the accuracy of the information recorded on the form with the corresponding source documents (Note: Source documents are not to be sent unless requested) and e-mail the form to the sponsor's Global Drug Safety Department. A copy of the sponsor's Clinical Study Serious Adverse Event and Non-serious AEs Required by the Protocol Form (and any applicable follow-up reports) must also be sent to the sponsor's Medical Monitor using the details specified in the emergency contact information section of the protocol.

Note: Minimum criteria for reporting an SAE are the SAE term, an identifiable subject, a suspect investigational medical product (study drug), and a reporter. Hospitalization is not an AE, but an SAE criterion. The SAE term is the medical event that led to the hospitalization. Surgery is not an AE, but the event that required the subject to have surgery is the SAE term. Death is not an SAE, but an outcome.

Autopsy reports, if applicable, will be forwarded as they become available. All pertinent laboratory results should be entered on the SAE form.

All SAEs must be reported, whether or not they are considered causally related to the study drug. Appropriate clinical, diagnostic, and laboratory measures should be performed to delineate the

cause of the SAE in question and the results reported. Follow-up for the SAE should occur at appropriate intervals until the event/laboratory abnormality:

- Returns to baseline or
- Becomes stable to a clinically acceptable level that is safe for the subject.

The investigator is required to assess the causal relationship of each reported SAE, to the study drug (see below). A causality assessment should always be included on the SAE form. The investigator should make the causality assessment based on the information available at the time of the event. The causality can be updated at a future date if additional information is received.

The investigator should decide whether, in his or her medical judgment, there is a reasonable possibility that the event may have been caused by the investigational product. If there is no valid reason for suggesting a relationship, then the event should be classified as “not related.” Otherwise, if there is any valid reason, even if undetermined or untested, for suspecting a possible cause-and-effect relationship between the investigational product and the occurrence of the event, then the event should be considered “related.” The causality assessment must be documented in the source document.

The following additional guidance may be helpful:

Term	Relationship Definition
Related	The temporal relationship between the event and the administration of the investigational product is compelling and/or follows a known or suspected response pattern to that product, and the event cannot be explained by the subject’s medical condition, other therapies, or accident.
Not Related	The event can be readily explained by other factors such as the subject’s underlying medical condition, concomitant therapy, or accident and no plausible temporal or biologic relationship exists between the investigational product and the event.

Contact information for SAE reporting and emergency contact details can be found at the beginning of the protocol.

As required by ICH guidelines and global health authorities, the sponsor or designee will notify investigators of all adverse drug reactions that are serious, unexpected, and deemed by the reporting investigator or sponsor to be related to study drug (suspected, unexpected, serious, adverse reaction [SUSAR]). Causality, while assessed, does not negate reporting requirements to the sponsor. An AE, whether serious or not serious, is designated unexpected (unlabeled) if it is not in the appendix to the Investigator Brochure (IB) that contains the compound adverse drug reactions; or if the event is of greater frequency, specificity, or severity than is recorded in the

IB. The investigator will receive a copy of the current valid version of the IB prior to the start of the study. The investigator will not be required to assess expectedness, nor should expectedness impact the investigator reporting SAEs within the timeframe herein defined.

The investigator should also comply with the Institutional Review Board (IRB) procedures for reporting any other safety information (eg, autopsy reports).

The sponsor or its designee will be responsible for submitting SUSAR reports to the appropriate health authorities. These reports will be submitted within the expedited timeframe.

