### 6.2.1.2 Procedures for Reporting Adverse Events

Adverse events may be spontaneously reported by the subject, obtained through nonleading questioning, or noted during examination of a subject. Adverse events will be recorded from the signing of the ICF and for the duration of the study. Adverse events that are not resolved at the end of study will be monitored with a telephone call by the investigator, as necessary, for approximately 4 weeks after the last dose of study drug or until resolution or until the AE is judged by the investigator to have stabilized.

As they occur, new AEs will be recorded sequentially on the AE page of the CRF. The AE term should note the diagnosis whenever possible, not the individual signs or symptoms (eg, myocardial infarction should be recorded rather than chest pain, elevated cardiac enzymes, and abnormal ECG). Also recorded are:

- Start and stop date and time (date the site becomes aware of the SAE)
- Whether the event is continuing
- Frequency (intermittent, continuous)
- Intensity (mild, moderate, severe)

- Mild: usually transient, requiring no special treatment and generally not interfering with usual daily activities
- Moderate: usually ameliorated by simple therapeutic maneuvers and impairs usual activities
- Severe: requires vigorous therapeutic intervention and interrupts usual activities. Hospitalization may or may not be required
- Relationship to study drug (not related, related): identify relationship as “related” if a causal relationship between the investigational product and an AE is at least a reasonable possibility (see Section [6.2.2.2](#) for additional guidance on relationship to study drug)
- Whether the AE is serious (ie, an SAE). If identified as an SAE, the AE should be reported on the SAE form according to Section [6.2.2](#) below.
- Actions taken (none; study drug dose changed, interrupted, or discontinued; other medication change; nondrug therapy)
- Outcome (not recovered/not resolved, recovered/resolved, recovered/resolved with sequelae, recovering/resolving, unknown, fatal). An individual AE receives only one outcome.

Laboratory values, blood pressure, ECG evaluations, and clinical findings at the scheduled physical examinations must be reported as AEs if they:

- Are considered clinically significant by the investigator (ie, not part of the subject’s medical history),
- Fulfill SAE criteria, and/or
- Cause subject discontinuation from the study.

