### 8.3.1 Statistical Methods for Safety Variables

Adverse events will be coded using the most recent version of the MedDRA dictionary. Treatment-emergent AEs will be summarized by system organ class and preferred term using descriptive statistics (eg, number and percentage of subjects). Adverse events will be summarized by severity, relationship to treatment, AEs leading to discontinuation, and AEs leading to death. SAEs will also be tabulated by overall and treatment-related events.

For laboratory tests, 48-hour urine output, vital signs, body weight, BMI, and ECG variables, descriptive statistics (eg, n, mean, standard deviation, median, minimum and maximum values, the number and percentage of subjects in specified categories) will be used to summarize the absolute values and change from Baseline at each time point.

The number and percentage of subjects classified as having antibodies to teduglutide will be used to summarize the presence of antibodies.

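### The causality table in Protocol Section 6.2.2.2 contradicts the decision rule above it and leaves events with both a plausible drug link and a competing explanation unclassified

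*Protocol*

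**What the plan says.** The references are to the current four-stage text of the protocol.

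- **Section 6.2.1.2 (all AEs).** The scale has two codes, not related and related. An event is related if a "causal relationship between the investigational product and an AE is at least a reasonable possibility". The section then refers the investigator to Section 6.2.2.2 for further guidance.
- **Section 6.2.2.2, decision rule.** An event is coded not related only where the investigator has no valid ground for suspecting the drug. The bar for the other code is low. It is met "if there is any valid reason, even if undetermined or untested, for suspecting a possible cause-and-effect relationship between the investigational product" on one side and what happened to the subject on the other.
- **Section 6.2.2.2, table, *Related* row.** The row has two parts. The first concerns timing or pattern: the temporal link "is compelling and/or follows a known or suspected response pattern to that product". The second is a further requirement on top of the first: "and the event cannot be explained by the subject’s medical condition, other therapies, or accident".
- **Section 6.2.2.2, table, *Not Related* row.** The event is readily explained by other factors, "and no plausible temporal or biologic relationship exists between the investigational product and the event".
- **Section 8.3.1 (use of the code).** "Adverse events will be summarized by severity, relationship to treatment, AEs leading to discontinuation, and AEs leading to death". SAEs are tabulated overall and for treatment-related events.

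The table is introduced as additional guidance that may help. No order of precedence between rule and table is stated.

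**The concern.** One binary code is governed by two tests that do not agree. The decision rule and Section 6.2.1.2 set a low threshold, under which a competing explanation does not exclude the drug. The *Related* row makes the absence of any other explanation a necessary condition. Because Section 6.2.1.2 sends all AEs to this guidance, the conflict is not confined to SAEs.

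Subjects are selected for short bowel syndrome and dependence on parenteral support, so a disease- or support-based explanation may be available for some events in which the drug is also suspected. The superseded three-stage text in the same file had a separate category for events that concurrent disease could also explain. The current section has none. That change is not itself an error, but the two-code guidance now has to place those events, and it does not.

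The study is uncontrolled, so no comparator arm shows how often such events would occur without the drug. If investigators use different parts of Section 6.2.2.2, like events can receive different codes. Where the *Related* row is used, the related subsets can be understated.

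**Working it through.** The plan gives no figure to reproduce on this point; the check is one of logic. Two questions are crossed: is there a plausible reason to suspect the drug, and can the event be explained by the subject's condition, another therapy or an accident? The rule and the two table rows are then applied to each combination.

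| Drug plausibly suspected | Otherwise explainable | Decision rule (6.2.2.2) | *Related* row | *Not Related* row |
|---|---|---|---|---|
| Yes | No | Related | Met, if timing is compelling or the pattern is known or suspected | Not met |
| Yes | Yes | Related | Not met, because the event can be explained | Not met, because a plausible link exists |
| No | Yes | Not related | Not met | Met |
| No | No | Not related | Not met | Not met, because there is no ready explanation |

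The rows are not complements: the second and fourth combinations fit neither.

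The second combination matters most. The rule says related and the *Related* row says the criterion fails. The *Not Related* row also fails, since it requires that "no plausible temporal or biologic relationship exists between the investigational product and the event". The table therefore gives no code. An investigator who works only from the *Related* row has one code left, not related, which is the opposite of the rule.

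Size, for illustration only. With N subjects, recoding the only related event of one subject changes the related-event incidence by 1/N. At the stated minimum of 5 (Section 4.1), 1/5 = 20 percentage points. With more subjects the shift per recoded subject is smaller. This says nothing about how many subjects would be affected.

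**The case against.** The case against giving this weight is substantial, and most of it stands.

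- **The rule is directive and the table is not.** The decision rule says how the event should be coded, and Section 6.2.1.2 sets a consistent low threshold. The table is only offered as possibly helpful. A reader who finds that an event fits neither row can go back to the rule and code it related. This stands as a limit on the consequence. It does not remove the contradiction, because no precedence is stated.
- **The table does not direct such events to not related.** A reader might infer that it does. The *Not Related* row rules that out when a plausible link exists, and the pattern test in the *Related* row accepts a suspected pattern as well as a known one. Miscoding is possible, not mandated.
- **The affected event is not shown to be the typical one.** A reader might join the admissions that Exclusion 15 lists as related to short bowel syndrome or parenteral nutrition with the growth effects in Sections 1.1 and 6.2.3, and conclude that most gastrointestinal, biliary, infectious or electrolyte events are exposed. None of these sections places one event in both lists, so the frequency is unknown.
- **Safety reporting is largely protected.** A reader might infer that expedited reporting fails. Section 6.2.2.2 requires all SAEs to be reported whatever their causality, allows the sponsor as well as the investigator to judge an event related for SUSAR purposes, and lets causality be updated. Section 6.2.3 requires special-interest AEs to be notified within 24 hours without a causality condition.
- **Withdrawal does not turn on the code alone.** Section 4.4.1 says listed events may lead to withdrawal. Its related-SAE item also requires that symptomatic treatment has not helped, and a separate item covers significant AEs regardless of causality.
- **Overall tables are unaffected.** Section 8.3.1 summarises all treatment-emergent AEs and all SAEs; only the related subsets depend on the code.

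What remains is the related subsets. For non-serious AEs outside special interest the protocol states no sponsor check of causality, so these safeguards do not reach that part of the related-AE tables.

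**Conclusion.** The *Related* row contradicts the decision rule above it and the reasonable-possibility test in Section 6.2.1.2. Events with a plausible drug link and a competing explanation have no row in the table, and an investigator relying on the *Related* row could code them not related.

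The exposure is inconsistent or understated related-AE and treatment-related SAE tabulations, together with the investigator's part of SUSAR identification. It does not extend to overall AE or SAE incidence, SAE reporting to the sponsor or special-interest notification. No endpoint or sample size depends on it.

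The number of codes that would change cannot be derived from the protocol. The 20 percentage points are the effect of one recoded subject, assuming 5 subjects and that the recoded event was that subject's only related one; they are not a forecast. The conclusion rests on wording alone and needs no assumption about event rates. It is a wording conflict in a reported safety variable that should be corrected.

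**What to change.** Delete the two-row table in Section 6.2.2.2, or rewrite its rows as exact complements under the existing rule:

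- *Related*: there is a reasonable possibility, on any valid ground for suspicion, that the product caused the event. An alternative explanation does not by itself make the event not related.
- *Not Related*: there is no valid ground for suspecting the product.

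State that this single rule applies to AEs under Section 6.2.1.2 and to SAEs under Section 6.2.2.2.

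The cost is one wording change and a memo to sites. The downside is a possibly somewhat higher count of related events. No visit, assessment, endpoint or planned table changes.

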### **6.2.3 Adverse Events of Special Interest**

An AE of special interest is an AE (serious or nonserious) of scientific and medical concern specific to the sponsor's product or program and for which ongoing monitoring and immediate notification by the investigator to the sponsor is required.

The AEs of special interest that require expedited regulatory reporting for this study include the following:

- Growth of pre-existing polyps of the colon
- Benign neoplasia of the GI tract including the hepatobiliary system
- Tumor-promoting ability (eg, benign and/or malignant neoplasia of any kind, not limited to those of the GI or hepatobiliary system)

For AEs of special interest, the Shire Global Drug Safety Department must be informed within 24 hours of first awareness as per the SAE notification instructions described in Section [6.2.2.2](#) even if the event does not fulfill seriousness criterion.

### **6.2.4 Pregnancy Reporting**

All pregnancies are to be reported from the time informed consent is signed until the defined follow-up period stated in Section [3.2](#).

Any report of pregnancy for any female study participant must be reported within 24 hours to the Shire Global Drug Safety Department using the Shire Investigational and Marketed Products Pregnancy Report Form. A copy of the Shire Investigational and Marketed Products Pregnancy Report Form (and any applicable follow-up reports) must also be sent to the CRO/Shire Medical Monitor using the details specified in the emergency contact information section of the protocol. The pregnant female study participant must be withdrawn from the study.

Every effort should be made to gather information regarding the pregnancy outcome and condition of the infant. It is the responsibility of the investigator to obtain this information within 30 calendar days after the initial notification and approximately 30 calendar days postpartum.

Pregnancy complications such as spontaneous abortion/miscarriage or congenital abnormality are considered SAEs and must be reported using the Shire Clinical Study Serious Adverse Event

and Non-serious AEs Required by the Protocol Form. Note: An elective abortion is not considered an SAE.

In addition to the above, if the investigator determines that the pregnancy meets serious criteria, it must be reported as an SAE using the Shire Clinical Study Serious Adverse Event and Non-serious AEs Required by the Protocol Form as well as the Shire Investigational and Marketed Products Pregnancy Report Form. The test date of the first positive serum/urine  $\beta$ -hCG test or ultrasound result will determine the pregnancy onset date.

### 6.2.5 Laboratory Evaluations

Laboratory results can vary depending on whether samples are drawn on an on- or off-PN/I.V. day, so it is important that every effort be made to draw laboratory samples on the same type of infusion day (ie, on- or off-PN/I.V.) throughout the study. Although subjects do not need to be in a fasted state at the time of their clinic visit, they should avoid large meals or large volumes of fluid, including PN/I.V. with lipids, within 3 hours of the clinic visit to permit consistent assessment. If peripheral venous access is not possible, the sample may be drawn from the central line. A home nursing visit may be appropriate to collect samples in some circumstances. The site's clinical laboratory will centrifuge and send the samples to the central lab, SRL Medisearch Inc. to be analyzed. Citrulline, antibody, and PK samples will be handled according to procedures specified in the laboratory manual.

Clinically significant (as determined by the investigator) abnormal laboratory test results will be considered AEs if they are not related to the subject's underlying condition or their previous comorbid medical history (unless they are a worsening of the condition). A result outside of the normal range may be repeated for confirmation. Any laboratory test result that meets the criteria for an SAE (Section 6.2.2) must also be recorded in an SAE Form so that the sponsor or designee can collect additional information about that abnormality, including information regarding relationship to investigational product or other causes, any action taken, and outcome.

The following laboratory parameters will be collected according to the Schedule of Evaluations and Procedures outlined in [Table 6-1](#), [Table 6-2](#), [Table 6-3](#), and [Table 6-4](#):

- Hematology

Hemoglobin, hematocrit, erythrocyte count, platelet count, and leukocyte count with differential

- Serum chemistry

Albumin; alkaline phosphatase; ALT; amylase; AST; total, direct, and indirect bilirubin; blood urea nitrogen; calcium; chloride; total-cholesterol; C-reactive protein; creatinine; creatinine clearance; gamma glutamyl transferase; glucose; lipase; magnesium; phosphate; potassium; sodium; triglycerides; and uric acid

- Urinalysis

Blood, glucose, leucocytes, microscopic, pH and osmolality, protein, and sodium

- Pregnancy test

Urine pregnancy test (women of childbearing potential [WOCBP] only)

- Antibodies to teduglutide and ECP

Blood samples for analyses of antibodies to teduglutide and to ECP will be collected at baseline and at Weeks 12 and 24 (or early termination) during Stage 2 of the study; at Months 6, 12, 18, and 24 (or early termination) during Stage 3; and at every other visit (every 6 months) and end-of-study (or early termination) visit during Stage 4. Blood sample for antibody testing is to be collected at study site prior to first investigational product administration. Once the subject has started teduglutide treatment, samples must be drawn at least 14 hours after dosing.

Antibody testing is a 3-step process. If a sample tests negative, no further testing is done. If a sample tests positive, further testing is done for teduglutide-specific antibodies. If teduglutide-specific antibodies are detected, the test is deemed “positive” and the titer derived, and neutralizing antibody testing is done. Subjects who test positive for teduglutide-specific antibodies may remain on treatment and blood samples for antibody testing will continue to be collected as per protocol schedule.

Blood samples for anti-teduglutide antibody testing may be stored and then analyzed together periodically to streamline the testing procedure. However, if an investigator suspects that a subject is experiencing an AE that may be associated with the development of anti-drug antibodies, relevant samples will be tested for the presence of anti-drug antibodies upon request.

